Automated data from the HIRD will be linked to the US National Death Index (NDI) to ascertain mortality endpoints, including all-cause mortality and mortality specific to study endpoints of interest. Medical records (for a random sample of 400 potential cases) will be used to refine and validate algorithms for identification of the primary endpoints (endometrial hyperplasia and endometrial cancer). For development of the endometrial endpoint algorithms, clinical evidence available in the medical record, which includes all results of endometrial biopsies and clinician evaluations, will be considered the gold standard definition of case status against which the claims-based algorithm's performance will be measured.

Study size: Hazard ratios (HRs) and their 95% confidence intervals (CIs) expected to be observed in this study were estimated. Endometrial hyperplasia and endometrial cancer are defined as the primary endpoints and were used for these calculations. The number of *Duavee* users in HIRD during the study period has been projected based on Pfizer commercial forecasts only; no patient data are currently available. Estimates of E+P HRT use were obtained based on pilot analyses of the HIRD from the last three years. For Year 1 of the US PASS, the 95% CI of the HR for the risk of endometrial hyperplasia is projected to lie between 0.44 and 2.26 (assuming the true HR=1.0) indicating that the study would be able to rule out an HR greater than 2.26. For Years 2 and 3, the CIs for endometrial hyperplasia risk in the study is projected to lie between (0.64 and 1.56), and (0.72 and 1.39), respectively. This indicates that the study would be able to rule out an HR greater than 1.56 at two years and greater than 1.39 at three years.

Data analysis: Analyses will focus on the comparison between women initiating either *Duavee* or E+P HRT. Baseline characteristics will be compared across the two cohorts of new users to assess potential confounding variables. For each safety endpoint (venous thromboembolism [VTE], stroke, coronary heart disease [CHD], breast cancer, ovarian cancer, endometrial hyperplasia, and endometrial cancer, etc.), univariate and adjusted HRs will be estimated that compare incidence of the first occurrence of each safety event between *Duavee* and E+P HRT users.

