4. MILESTONES

Milestone	Planned date
Updated FULL Draft Protocol submitted to CHMP/PRAC	10 October 2014
FINAL Draft Protocol Submission to EMA (for PRAC review)	26 January 2015
Update to FINAL Protocol in response to PRAC assessment	23 July 2015

Protocol Registration in the EU PAS register (upon endorsement from the PRAC/CHMP)	01 October 2015
Start of data collection ^a	01 May 2014
End of data collection ^b	01 May 2018
1 st Annual Study Report ^c	31 March 2016
2 nd Annual Study Report	31 March 2017
3 rd Annual Study Report	31 March 2018
FINAL Study Report	31 March 2019
Mortality Supplement to the FINAL Study Report	31 March 2021 ^d

a. This is a retrospective cohort study and the source data has been accruing since *Duavee* became available in the US in May, 2014. In accordance with EU Pharmacovigilance Guidance (Module VIII), the start of a PASS using secondary data is defined to be when the analytic dataset is extracted. This will not be done until the study protocol has been approved by the PRAC.

b. Study Period is from May 2014 through May 2018.

c. Time from US launch (May 2014) to First Annual Report is 23 months: 12 months is needed to accumulate one year of observation, a database lag of 4 months from real-time, and 7 months needed to extract data, perform analyses, and generate submission ready First Annual Report.

d. National Death Index data lags real-time by 18-24 months and is updated only once annually. Mortality follow-up will end May, 2018. See Figure 2 for further details.

CHMP = Committee for Medicinal Products for Human Use; EMA = European Medicines Agency; PAS = Post Authorization Studies; PRAC = Pharmacovigilance Risk Assessment Committee.

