7. RESEARCH METHODS

7.1. Study Design

This PASS is a retrospective cohort study utilizing a healthcare claims data source (HIRD) in the US. Two (2) treatment groups (*Duavee* and E+P HRT) will be identified, followed, and reported upon using annual database updates. A new-user cohort design will be used for the main analysis and users with a history of (E+ P) HRT will be examined in sub-analyses. The study will accumulate data for 4 years (May, 2014-May, 2018) as it follows a dynamic cohort of patients that enter the study at different times, based on when *Duavee* or E+P HRT is initiated.

Figure 1 shows the length of study follow-up according to when new users enter the cohort.

The study duration was determined based on sample size calculations, and is the soonest that clinically meaningful HRs for endometrial hyperplasia and endometrial cancer can be detected. Study years and reporting intervals will run from May 1 through April 30 of the next year. Interim (follow-up) and final reports will contain both interval and cumulative data.

All patients in the HIRD who initiate *Duavee* or E+P HRT in the study period (2014-2018) will be considered for inclusion. This PASS is a retrospective cohort study using secondary data. The source data has been accruing since *Duavee* became available in the US in May, 2014. In accordance with EMA Pharmacovigilance Guidance (Module VIII)⁵, the start of a PASS using secondary data is defined to be when the analytic dataset is extracted. This will not be done for this PASS until the study protocol has been approved by the PRAC.

Follow-up will continue from the first use of *Duavee* or E+P HRT through to the earliest of the following censoring events:

- End of continuous health plan eligibility;
- Switch from *Duavee* to an E+P HRT medication or vice-versa;
- (Note: Any use of an estrogen or estrogen-containing product (Appendix 2) that differs from the HRT treatment regimen dispensed on the index date will censor follow-up. This does not include dispensing of a topical estrogen that is a single-unit

E+P HRT. As described in [Section 7.7.4](#), sensitivity analyses exploring the impact of this criterion will be performed.

- First occurrence of a safety endpoint.

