7.5. Study Size

The focus of the sample size calculations is to determine the precision of the estimated HR that can potentially be achieved in the study depending on estimated patient accrual, event rates, and assumed true risk. Because of the CHMP’s concerns related to endometrial safety, endometrial hyperplasia and endometrial cancer are the primary endpoints and were used for these sample size calculations.

Precision is a measure inversely related to variance in estimation. For the HRs being estimated in this study, precision is represented by the width of two-sided 95% CI.

Duavee estimates are projections based on Pfizer commercial forecasts of product uptake only; no patient data are yet available. Projections are conservative and assume a reduction of 50% from the original US market forecasts. The estimated number of E+P HRT new users, their total person-time of follow-up, and the expected number of incident endometrial safety events observed in that cohort was obtained based on pilot analyses of the HIRD from the last three years. Therefore, the most recent 3 years of E+P HRT use in the HIRD is being used to project future E+P HRT uptake and use.

In the HIRD pilot analyses, the number of new users of E+P HRT products (i.e., patients with at least 12 months of continuous eligibility prior to the first use of E+P HRT) were identified using a one-, two-, and three-year time frame: 01 January 2011 – 31 December 2011, 01 January 2011 – 31 December 2012, and 01 January 2011 – 31 December 2013. The total person-time of follow-up accrued by the E+P HRT new users was calculated during these periods of interest together with the number of endometrial cancer and endometrial hyperplasia events occurring after the start of E+P HRT use.

All estimates (Table 1) were calculated with two-sided 95% CIs. According to the study plan, there will be a 4-year accrual period and patients will be followed for at least 1 year, with the first two cohorts being followed for a longer duration.

Table 1. Estimated 95% Confidence Intervals for Hazard Ratios of Endometrial Safety

Description	First Annual Report	Second Annual Report	Third Annual Report
Estimated numbers of new users of Duavee ^a	1,800	3,600	5,400
Estimated numbers of new users of E+P HRT ^b	36,651	44,122	50,350
Estimated person-years of follow-up for E+P HRT users ^b	27,768	58,399	89,438
Estimated endometrial cancer events after the start of E+P HRT use ^b	29	62	80
HRs (95% CI)			

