Table 1. Estimated 95% Confidence Intervals for Hazard Ratios of Endometrial Safety

Description	First Annual Report	Second Annual Report	Third Annual Report
true HR=1.0	(0.18, 5.60)	(0.39, 2.56)	(0.48, 2.10)
true HR=1.5	(0.36, 6.33)	(0.68, 3.33)	(0.80, 2.83)
Estimated endometrial hyperplasia events after the start of E+P HRT use ^b	129	274	399
HRs (95% CI)			
true HR=1.0	(0.44, 2.26)	(0.64, 1.56)	(0.72, 1.39)
true HR=1.5	(0.76, 2.96)	(1.03, 2.19)	(1.13, 1.99)

a. *Duavee* estimates are projections based on Pfizer commercial forecasts of uptake only, no patient data are yet available. Person-time was calculated based on the assumption of 10 month treatment duration per patient⁹. Projections are conservative and assumed a reduction of 50% from actual US market forecasts.

b. E+P HRT users, person-time, and event estimates are derived from pilot analyses of the HIRD from the last three years of data.

Based on the projected numbers of patients initiating *Duavee* and E+P HRT as shown, for Year 1 of the US PASS, the estimated 95% CI of the HRs for the risk of endometrial hyperplasia in Table 1 imply that if the underlying (true) HR comparing *Duavee* users to E+P users is HR=1.0, then the point estimate of HR in the study will lie between 0.44 and 2.26, indicating that the study would be able to rule out the possibility that the true HR is greater than 2.26.

For Years 2 and 3, the estimated 95% CIs of the HRs for the risk of endometrial hyperplasia in Table 1 imply that if the underlying (true) HR comparing *Duavee* users to E+P users is HR=1.0, then the point estimates of HR in the study will lie between (0.64 and 1.56), and (0.72 and 1.39), respectively. This indicates that the study would be able to rule out the possibility that the true HR is greater than 1.56 at two years and 1.39 at three years.

These estimates are dependent on actual future E+P and *Duavee* drug uptake, the speed of patient accrual, safety event rates, and patient follow-up time; if these differ substantially from our estimates, then the precision of the HRs may change.

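### Table 1 does not use the 10-month Duavee person-time it cites, and its Year 1 precision (HR above 2.26 ruled out) needs more follow-up per Duavee user than even entry over the 12-month window would give

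*Protocol*

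**What the plan says.** Section 7.5 projects precision for three annual reports. It states that "All estimates (Table 1) were calculated with two-sided 95% CIs". Cumulative new users are "1,800 3,600 5,400" for Duavee and "36,651 44,122 50,350" for E+P HRT. For Year 1 the E+P cohort contributes 27,768 person-years, 129 hyperplasia events and 29 endometrial cancer events.

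On Duavee follow-up, footnote a to Table 1 says: "Person-time was calculated based on the assumption of 10 month treatment duration per patient". The text before the table adds that patients will have a minimum of one year of follow-up.

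For Year 1 hyperplasia at a true HR of 1.0, section 7.5 says that "the point estimate of HR in the study will lie between 0.44 and 2.26". The abstract repeats the interval, "indicating that the study would be able to rule out an HR greater than 2.26".

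The Year 1 window is set elsewhere. Section 7.1: "Study years and reporting intervals will run from May 1 through April 30 of the next year". Section 4, footnote c, counts from the May 2014 US launch: "12 months is needed to accumulate one year of observation"; the other 11 months before the first report are database lag and report preparation. Section 7.1 also censors patients at the end of the period covered by each interim report.

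**The concern.** No woman can start Duavee before launch, and launch opens the Year 1 window. Users who enter during those 12 months have anything from 12 months down to no potential follow-up at the cut. Neither the 10 months in footnote a nor a one-year minimum fits that window unless most users start very soon after launch. If the printed intervals rest on similar amounts of Duavee follow-up, the Year 1 precision is too favourable.

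That precision is a headline figure in the abstract and in section 7.5. A regulator reading the first interim report would set the observed interval against it. For endometrial cancer, the expected number of Duavee events in Year 1 could be below one.

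**Working it through.** **Inputs (Table 1, Year 1).** Duavee users 1,800. E+P users 36,651, with 27,768 person-years, so 27,768/36,651 × 12 = 9.1 months each. E+P events: 129 hyperplasia (4.65 per 1,000 person-years) and 29 cancer (1.04 per 1,000). Intervals are HR × exp(±1.96 × SE).

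**Step 1: reproduce the printed intervals.** Let p = Duavee users/(Duavee + E+P users), q = HR·p/(HR·p + 1 − p), D = the tabulated E+P event count treated as the total, and SE = 1/√(D·q·(1 − q)).

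Year 1: p = 1,800/38,451 = 0.0468.

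| Year 1 | Formula | Printed |
|---|---|---|
| Hyperplasia, HR 1.0 | (0.442, 2.264) | (0.44, 2.26) |
| Hyperplasia, HR 1.5 | (0.758, 2.969) | (0.76, 2.96) |
| Cancer, HR 1.0 | (0.179, 5.601) | (0.18, 5.60) |
| Cancer, HR 1.5 | (0.355, 6.329) | (0.36, 6.33) |

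The Year 2 and Year 3 intervals also agree to about 0.01; for example, Year 3 hyperplasia at HR 1.0 gives (0.718, 1.393) against (0.72, 1.39). Duavee person-time does not enter this formula.

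**Step 2: try footnote a as written.** Ten months × 1,800 users = 1,500 person-years. This gives 1,500 × 129/27,768 = 6.97 Duavee hyperplasia events, SE = √(1/6.97 + 1/129) = 0.389, and an interval of (0.47, 2.14). The printed interval is not recovered.

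**Step 3: Duavee follow-up implied by the printed intervals.** SE = ln(U/L)/(2 × 1.96); Duavee events d = 1/(SE² − 1/E+P events); person-years = d/(HR × E+P rate).

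| Year 1 | d | Person-years | Months per user |
|---|---|---|---|
| Hyperplasia, HR 1.0 | 6.0 | 1,293 | 8.6 |
| Hyperplasia, HR 1.5 | 8.9 | 1,275 | 8.5 |
| Cancer, HR 1.0 | 1.36 | 1,304 | 8.7 |
| Cancer, HR 1.5 | 2.0 | 1,276 | 8.5 |

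Working from the upper limit alone moves the lowest value to 8.4. If the 129 events are read as the total, the E+P share is about 123 and the implied figure is 9.1 months, the E+P mean. The range is therefore about 8.4 to 9.1 months.

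**Step 4: what the window allows.** Even entry over 12 months with censoring at month 12 gives a mean of 6 months with no losses: 1,800 × 0.5 = 900 person-years. With 10% or 20% annual disenrolment (illustrative values) the mean is 5.8 or 5.6 months. Only 2/12 = 17% of users could be observed for 10 months. If uptake rises linearly from zero at launch, mean entry is at month 8 and mean follow-up is 4 months, or 600 person-years. A mean of 8.6 months needs a mean entry 12 − 8.6 = 3.4 months after launch, with no disenrolment.

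**Step 5: Year 1 recomputed.** d = HR × E+P rate × Duavee person-years; SE = √(1/d + 1/E+P events).

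| | Printed | 900 person-years | 600 person-years |
|---|---|---|---|
| Hyperplasia, HR 1.0 | (0.44, 2.26) | d = 4.2: (0.38, 2.65) | d = 2.8: (0.31, 3.28) |
| Hyperplasia, HR 1.5 | (0.76, 2.96) | d = 6.3: (0.67, 3.34) | d = 4.2: (0.57, 3.97) |
| Cancer, HR 1.0 | (0.18, 5.60) | d = 0.94: (0.13, 7.8) | d = 0.63: (0.08, 12.2) |

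With so few events the normal approximation is rough, but it is the same kind of approximation that reproduces the printed figures, so the comparison is like with like.

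**The case against.** The protocol gives no within-year entry pattern for Duavee, and the forecast behind the 1,800 users is not shown. A mean above 6 months is therefore not impossible, and the protocol's own E+P cohort averages 9.1 months in a 12-month window. This stands to the extent that 6 months must be presented as conditional on even entry. The E+P pattern does not carry over readily, however: that cohort is strongly front-loaded, with 36,651 users in the first year and only 44,122 − 36,651 = 7,471 added in the second, whereas Duavee has no users on the first day and is projected at a level 1,800 a year. Section 7.9 itself allows for limited first-year uptake.

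The 1,800 is described as half the market forecast. With 3,600 users and 6 months each, the hyperplasia interval at HR 1.0 would be (0.50, 2.01), tighter than printed. That shows the projection may prove pessimistic on user numbers. It does not make the interval correct for the 1,800 users to which it is attached.

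Section 7.5 warns that precision may change if accrual or follow-up differs from the estimates. That covers departures from the assumptions; it does not cover a table that departs from its own stated assumption and sits uneasily with its own window.

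The printed cancer interval is already wide, and section 7.7.6.2 withholds any HR until each cohort has an event and there are at least four in total. Both points are fair and limit what the cancer figures add. The study also aims at estimation rather than testing, and Year 1 is only the first of three interim reports.

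**Conclusion.** The point holds in conditional form. Table 1 is reproduced without any Duavee person-time, so footnote a does not describe how the intervals were obtained; the head-count formula is inferred from this agreement, since the protocol does not print one. Its effect is to give Duavee users E+P-like follow-up. In Year 1 that is about 8.4 to 9.1 months per user, against at most 6 under even entry with no early entry surge. On that assumption the hyperplasia upper limit at HR 1.0 moves from 2.26 to about 2.65, and the cancer upper limit from 5.60 to about 7.8; at a mean of 4 months they are about 3.3 and 12.2. The effect on an interim projection is moderate.

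A reader might infer three stronger things, none of which the documents support:

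- That 6 months is a hard maximum. It holds only for even or later entry, and the entry pattern is not stated.
- That Year 1 is a different error from the later columns. The same formula reproduces all three, and Years 2 and 3 imply about 14.8 and 19.4 months per Duavee user (hyperplasia, HR 1.0), also at odds with footnote a.
- That 2.26 is the benchmark for extending the study. Section 7.9 says that uptake will be evaluated at the end of Year 1 and names no precision threshold.

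**What to change.** - Recompute all of Table 1 from explicit Duavee person-time, with a stated entry assumption and censoring at each 30 April cut. For Year 1, use 900 person-years under even entry and add a slower-uptake row near 600. Treat the last-entered year in the later columns in the same way.
- State the interval formula under the table.
- Reconcile footnote a, and the sentence promising at least a year of follow-up, with that calculation.
- Replace the Year 1 statements on ruling out an HR above 2.26 in section 7.5 and the abstract. Under even entry the intervals at HR 1.0 are about (0.38, 2.65) for hyperplasia and (0.13, 7.8) for endometrial cancer.

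The cost is a recalculation and edited figures in Table 1, section 7.5 and the abstract. The stated interim precision becomes less favourable. Study conduct is unchanged.

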7.6. Data Management

[figure not shown]
All data management and analyses will be conducted by HealthCore in accordance with their standard operating procedures (SOPs) and guidelines. The study database, analytic files, and statistical programming will be documented in a Project Log, stored electronically, and archived for a period of six years following the delivery of the final study report unless otherwise noted. De-identified and aggregated results will be reported to Pfizer.

7.7. Data Analysis Plan

This overview details the major steps that will be performed to produce the analytic dataset, generate study results, and apply those results to the research objectives in accordance with

the European Network of Centres for Pharmacoepidemiology and Pharmacovigilance (ENCePP) Guide on methodological standards in pharmacoepidemiology (Chapter 7- Statistical and Epidemiological Analysis Plans).¹⁰

Figure 4. Analysis populations

7.7.1. Main Analyses

The analyses will describe patients that initiate *Duavee* and the comparator E+P HRT cohort with respect to demographic and clinical characteristics as enumerated in [Section 7.3.4](#). Reasons for censoring will also be described by exposure group. Descriptive comparisons of the two cohorts will be done to document their differences at baseline and to identify potential confounders to be addressed in the propensity matching.

For each of the primary endpoints (i.e., endometrial hyperplasia and endometrial cancer), an IR will be calculated as the number of women meeting a claims-based algorithm for each outcome (first event only) divided by person-time at risk.

The IR and its associated 95% CI will be presented for each cohort overall and stratified by categorical patient age at cohort entry, total duration of *Duavee* or E+P HRT treatment (long vs. short), time since last exposure to *Duavee* or E+P HRT, exposure to local hormone therapy (See Appendix 2), and by presence (Y/N) of an osteoporosis diagnosis within the 90 days before or after initiation of *Duavee* or E+P HRT. Duration of treatment and time since last exposure will be categorized based on observed data distributions. The feasibility of these stratifications and of a possible analysis that stratifies simultaneously by duration of treatment and time since last exposure will be determined based on the number of observed safety events.

Further details of the validation process are described in Appendix 3 and will be contained in the separate Endpoint Algorithm Development Report.

Hazard ratios will be estimated that represent the relative risk associated with initiating *Duavee* as compared to E+P HRT. It is planned to conduct both crude (unadjusted) and adjusted analyses to assess the HR for each of the primary endpoints. Adjusted analyses will use propensity score matching to ensure comparability between treatment groups. Further discussion of the methods to be used in computing propensity scores is included in [Section 7.7.3](#).

Similarly to the primary endpoints, the IR and multivariate adjusted HR will be calculated for the following *a priori* defined secondary safety endpoints: VTE, stroke, CHD, breast cancer, ovarian cancer, thyroid cancer, renal cancer, renal adenoma, gastrointestinal tract cancers, all cancers and all-cause mortality among study subjects initiating *Duavee* or E+P HRT. Because only the primary endpoints are being validated as part of this project, positive predictive value (PPV) correction of IR estimates for secondary endpoints will not be performed.

For all analyses, each endpoint will be identified first in the automated claims data (i.e., endpoints that were not fatal prior to the patient reaching the healthcare system) and then, for study reports that include NDI linkage, through either the automated data or the NDI (i.e., a composite of non-fatal and fatal endpoints, such as endometrial cancer and death due to endometrial cancer). Analyses that include NDI linkage will be restricted to the time period that is available in both the HIRD and NDI data sources (i.e., through the end of the 2016 calendar year if the first NDI search is performed in preparation for the Final Study Report).

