 - Once a patient has had a safety event, they will be censored from the analysis of that event only. For example, a patient for whom an endometrial hyperplasia outcome is identified will remain in follow-up for analysis of breast cancer (and endometrial cancer).
- End of the study period.
 - Patients will be censored by the end of the study period for each interim report and the final study report, however, additional follow-up time for these patients will be added during the subsequent study year.
- Occurrence of any type of cancer diagnosis;
 - As described in [Section 7.7.4](#), sensitivity analyses exploring the impact of this criterion will be performed.
- Hysterectomy;
 - Codes indicating a procedure for hysterectomy will be used to define this censoring criterion.
 - Presence of a code indicating post hysterectomy status (ICD-9-CM V88.01) or a hysterectomy procedure code at any time in the baseline or follow-up period will result in exclusion of the patient. The one exception is, when in the follow-up period, the procedure code precedes the hysterectomy status code (i.e., date of post-index hysterectomy is known); the patient's follow-up will be included, but censored on the procedure date.
- Death.

Discontinuation and/or resumption of *Duavee* or E+P HRT treatment will be defined and recorded, but follow-up will not be censored based on treatment discontinuation. Sensitivity analyses will be conducted to examine the impact of censoring based on (1) treatment switch and (2) cancer diagnosis. The Sponsor will also conduct sub-analyses for patients not included in the main analyses. These patient groups are those with either (1) use of E+P HRT (i.e., not new initiators), or (2) unopposed estrogen in their baseline period.

For each of the 4 study years, the Sponsor will: (1) identify and follow new *Duavee* or E+P HRT users; and (2) extend the follow-up to include newly available data covering any additional follow-up period for patients that were identified during previous study years.

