7.2.2. Exclusion Criteria

Patients meeting any of the following criteria will be excluded from the study:

- Patients with an insufficient period of enrollment prior to their index prescription (e.g., 6 or 12 months as determined prior to the start of analysis) will be excluded. This period is necessary to determine if the patient is a new initiator of *Duavee* or E+P HRT without a history of unopposed estrogen use, and also to adequately ascertain baseline covariates/patient history;
- Patients without a uterus, i.e., males, or women for whom evidence of hysterectomy is identified prior to initiation of *Duavee* or comparator E+P HRT; and
- Patients with a history of any type of cancer in their baseline period.
- Patients for whom *Duavee*, comparator E+P HRT or unopposed estrogen are identified during the baseline period will be excluded from the main analyses. They will be evaluated in separate sub-analyses.

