7.4. Time Periods

Each patient will have an index date corresponding to the date of their first prescription for *Duavee* or E+P HRT treatment after 01 May 2014. Baseline characteristics will be assessed from patient data collected prior to their index date (baseline period). A baseline period will be specified in a manner that balances inclusion of as many *Duavee* users as is feasible in the cohort with the need to ascertain covariates prior to the start of treatment. The baseline period will be determined prior to conducting analyses based on review of the distribution of prior continuous health plan enrolment among the *Duavee* cohort of patients.

As described in [Section 7.1](#), follow-up will continue from the first use of *Duavee* or E+P HRT through to the earliest occurrence of a censoring event.

[figure not shown]
Patients will accrue both person-time at risk and person-time on treatment. Analyses will consider patients at risk during the entirety of their follow-up until censoring, regardless of treatment discontinuation. Exploratory analysis will be done on the timing of events in relation to being on treatment.

Scenarios illustrating the duration of the follow-up period are presented in Figure 3.

[figure not shown]
Figure 3. Safety endpoints

- Key:**
- Enrolled in a health plan
 - Exposure to *Duavee*
 - ▨ Exposure to comparator E+P HRT

Patient A: *Duavee* cohort member censored due to use of a comparator E+P HRT

Patient B: E+P HRT cohort member censored due to end of health plan enrolment, history of MI diagnosed at baseline.

Data Source

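### The osteoporosis stratum in 7.7.1 uses diagnoses up to 90 days after person-time starts, so membership depends on remaining under observation, with a small effect limited to one descriptive rate

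*Protocol*

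**What the plan says.** Section 7.7.1 lists the factors by which each cohort's incidence rate will be stratified. One is "presence (Y/N) of an osteoporosis diagnosis within the 90 days before or after initiation of" Duavee or E+P HRT. The rate is first events divided by person-time at risk, and feasibility of the strata is to be judged from the number of events.

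Section 7.1 fixes the clock: "Follow-up will continue from the first use of *Duavee* or E+P HRT through to the earliest of the following censoring events". These events include loss of plan eligibility, switch, any cancer, hysterectomy and death. Reports also truncate: "Patients will be censored by the end of the study period for each interim report and the final study report", after which "additional follow-up time for these patients will be added during the subsequent study year". The cut-offs are annual: "Study years and reporting intervals will run from May 1 through April 30 of the next year".

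Two neighbouring definitions stop at initiation. Section 7.3.4 lists osteoporosis among conditions diagnosed in the baseline period, and 7.7.3 balances the cohorts at first dispensing. For the stratum, no landmark, lag, minimum follow-up or time-varying rule is stated.

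**The concern.** A fixed Y/N label set partly by what happens after time zero brings two problems.

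- **Immortal time.** A woman first coded on day 80 is Y from day 0. If she had to remain in follow-up until day 80 to be coded, those 80 days enter the Y denominator and could not have produced a Y event. Early events with no earlier diagnosis go to N.
- **Incomplete windows.** A woman who disenrolls, dies or reaches the report cut-off before day 90 cannot show a later diagnosis. If that would have been her only qualifying one, she is placed in N. At a cut-off she may move to Y in the next cumulative report, taking earlier person-time with her. For the last entrants before May 2018 there is no later report on non-fatal events to correct this.

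At stake is whether the Y and N rates can be compared with each other and from one report to the next.

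**Working it through.** The protocol gives no osteoporosis prevalence, no timing of diagnoses and no disenrollment rate, so there is no stated figure to reproduce. The size below rests on assumptions.

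**1. Which half of the window is at risk.** The look-back half is complete for everyone, because 7.2.2 excludes "Patients with an insufficient period of enrollment prior to their index prescription" and the examples given are 6 or 12 months, both longer than 90 days. Only the forward half can be cut short.

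**2. Entrants with an incomplete forward half at a cut-off**, with uniform entry within the study year and Table 1 counts:

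- Report 1, Duavee: 90/365 = 24.7%, or 444 of 1,800.
- Report 3, Duavee: 444/5,400 = 8.2% if Table 1 counts are cumulative. If they are annual, 5,400 × 90/365 = 1,332, and 1,332/10,800 = 12.3%.
- Report 3, E+P HRT: (50,350 − 44,122) × 90/365 = 1,536, and 1,536/50,350 = 3.1%.
- For E+P HRT in report 1, 24.7% is probably too high. Mean pilot follow-up was 27,768/36,651 = 0.76 years, against 0.5 under uniform entry without dropout.

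Disenrollment within 90 days adds 1 − (1 − r)^(90/365), which is 2.6% to 8.4% for an assumed r of 10 to 30% a year.

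**3. Y women placed in N.** Let f be the share of Y women whose only qualifying diagnosis is post-index (assumed 10 to 70%), with dates uniform over w = 90/365 = 0.2466 years. With entry uniform over L years and an assumed disenrollment hazard of 0.2 a year, the probability of still being observed t years after entry is S(t) = (1 − t/L)·exp(−0.2t). The chance that the diagnosis is seen is P = (1/w)∫₀ʷ S(t)dt = 0.856 for L = 1 and 0.946 for L = 4. The misplaced share of Y women is f(1 − P).

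**4. Y rate if diagnoses count only before the endpoint or censoring.** Per Y woman, in years:

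- M = ∫₀ᴸ S(t)dt, mean follow-up if diagnosed before initiation: 0.4683 (L = 1), 1.5583 (L = 4).
- I = (1/w)∫₀ʷ t·S(t)dt, immortal time if diagnosed after initiation: 0.0998, 0.1144.
- A = (1/w)∫₀ʷ∫ₜᴸ S(u)du dt, follow-up after that diagnosis: 0.3569, 1.4395.

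Observed/true Y rate = 1 − f·I / [(1 − f)M + f(I + A)], treating the endpoint as rare with a constant hazard. For f = 0.5 and L = 1: 0.0499/(0.2341 + 0.2283) = 0.108, so the ratio is 0.892.

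| f (assumed) | Rate ratio, year 1 | Rate ratio, 4 years | Y women put in N, year 1 | Y women put in N, 4 years |
|---|---|---|---|---|
| 10% | 0.979 | 0.993 | 1.4% | 0.5% |
| 30% | 0.936 | 0.978 | 4.3% | 1.6% |
| 50% | 0.892 | 0.963 | 7.2% | 2.7% |
| 70% | 0.848 | 0.948 | 10.0% | 3.8% |

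A simulation of 4 million women per scenario, with five times the pilot hyperplasia rate (129/27,768 person-years) for precision, agreed with these rate ratios to within 0.004.

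**5. Y rate if diagnoses count throughout enrollment.** The simulated ratio is 1.00 for every f, because an event no longer stops a woman being coded. The misplaced shares stay as in the table if claims after the cut-off are not used.

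**6. Size against chance.** With the 10-month treatment duration in the Table 1 footnote, 1,800 × 10/12 = 1,500 Duavee person-years. That gives 1,500 × 129/27,768 = 7.0 hyperplasia and 1,500 × 29/27,768 = 1.6 endometrial cancer events in year 1, before any split.

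**The case against.** The strongest reply is that the rate bias needs a reading the protocol does not state and, for hyperplasia, partly speaks against. Section 7.1 censors a woman with an event from that event's analysis only and keeps a hyperplasia case in follow-up for other endpoints. Switching or a cancer diagnosis ends analysis time but not enrollment, so claims to day 90 remain visible. This stands: the understated rate is conditional. It does not remove the loss through disenrollment, death or cut-off.

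The cut-off loss is conditional too. Under the 4-month database lag in Section 4, claims to late July would be available by late November, before a 31 March report. The protocol does not say whether they may be used to classify women.

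Stronger readings a reader might infer are not supported:

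- **That 7.7.1 contradicts 7.4.** Section 7.4 governs baseline characteristics. Section 7.7.1 never calls this stratum one, and lists it beside treatment duration and time since last exposure, which are post-index by design. The protocol has two differently defined osteoporosis variables.
- **That recent entrants are misclassified as a group.** The 24.7% counts incomplete windows. A woman diagnosed in the 90 days before initiation is correctly Y, and one with no diagnosis in the window is correctly N.
- **That the stratum represents the US-only osteoporosis indication.** No section says so, and the generalizability argument in 7.10 does not cite it.

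The consequence is also small against chance: with 3 events in the Y stratum, the exact 95% interval runs from about 0.21 to 2.9 times the estimate. That argues for low priority. It does not justify keeping a rule whose result depends on an unstated programming choice.

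**Conclusion.** The point holds as a minor defect in a stated rule. Membership uses information from inside follow-up, and women observed for under 90 days can be placed in N in every report, including the final one.

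If diagnoses count only before the endpoint or censoring, the Y rate is understated by about 2 to 15% in year 1 and 1 to 5% at four years. If they count throughout enrollment, there is no rate bias for non-fatal endpoints. About 1.4 to 10% of Y women in year 1 are still put in N when claims after the cut-off are not used. These ranges assume post-index shares of 10 to 70%, uniform entry, uniform diagnosis dates and a disenrollment hazard of 0.2 a year, none of which the protocol gives.

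The effect is confined to one descriptive stratification that is itself subject to feasibility. Overall incidence rates do not use the stratum, and the adjusted hazard ratios balance at first dispensing, so both are unaffected.

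**What to change.** In 7.7.1, keep the 90-day window but assign person-time and events to Y only from the later of initiation and the first qualifying diagnosis date, and to N before it. Status on any day then uses only what is already known, person-time already reported does not change stratum later, and the simulated Y-rate ratio is 1.00 even when diagnoses count only before the endpoint or censoring. The cost is one sentence and one split of follow-up per affected woman. Days before a post-index diagnosis then belong to N, which the table should state.

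Alternatively, define the stratum from diagnoses up to and including the index date. This is simpler and fixes membership at entry. The downside is that women first coded after initiation stay in N. The protocol does not give that share, and it could be substantial: on the assumptions above, up to 10 to 70% of Y women, less any recovered by a look-back longer than 90 days.
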